5.1.7.2 Technical Computational Details for Primary Outcome Analysis

- 1) Baseline for Treatment Phase B is the last evaluation of serum sodium at the end of Treatment Phase A.
- 2) For the Early Withdrawal group, the serum sodium collected at 72 hours post-last dose on the CRF will be used to define the endpoint of Treatment Phase B. For the Late Withdrawal group, the serum sodium collected at 24 hours post-dose (Trough) of Day 4 on the CRF will be used to define the endpoint of Treatment Phase B.
- 3) The MMRM analysis for the primary endpoint will be analyzed using PROC MIXED of SAS (with default REML option). Specifically, the following SAS statements will be used for the primary analysis:

```
proc mixed;
class treatment visit subject agesubgrp responsesubgrp etiologysubgrp;
model change =agesubgrp responsesubgrp etiologysubgrp treatment visit
treatment*visit baseline baseline*visit/ s ddfm=kr;
repeated visit / type=un sub=subject;
lsmeans treatment*visit / pdiff cl alpha=0.05;
run;
```
- 4) In case there is a convergence problem in the MMRM model with the unstructured variance covariance matrix, the following variance covariance matrix structures will be used in the order of 1) heterogeneous toeplitz, 2) heterogeneous autoregressive of order 1, and 3) heterogeneous compound symmetry. The first (co)variance structure which does not have a convergence problem will be the one used for the analysis. If a structured covariance has to be used, the “sandwich” estimator of the variance covariance matrix of the fixed effects parameters will be used in order to deal with possible model misspecification of the covariance matrix.
- 5) Medications for rescue therapy (with indication of hyponatremia) include:
Rescue therapy is defined as any level of fluid restriction, hypertonic saline, isotonic saline (with or without diuretic for purpose of increasing the serum sodium level), plasmapheresis/dialysis, demeclocycline, urea, lithium, commercially available

vaptans, or any treatment intended to raise the level of serum sodium at any time during the trial.

5.1.7.3 Subgroup Analysis of the Primary Outcome Endpoint

Subgroup analysis of the primary efficacy endpoint will be conducted by gender and race (white and all other races), using similar analysis of the primary analysis. The subgroup analysis by 3 stratification factors will also be provided for the primary endpoint.

Subgroup analysis by additional age categories [REDACTED]

[REDACTED] will also be provided for the primary endpoint.

5.1.8 Secondary Outcome Analyses

5.1.8.1 Analysis of the Key Secondary Endpoint

For all subjects, the key secondary endpoint is the change from baseline in serum sodium concentration at the end of Day 2 (or 2a) at the end of Treatment Phase A. The analysis of the key secondary endpoint will be based on the Treatment Phase A Efficacy Sample.

A paired Student's t-test will be used to analyze the key secondary endpoint.

For the key secondary efficacy analysis, a hierarchical testing procedure will be used to maintain the overall experiment-wise type I error rate at 0.05. Thus, if the primary efficacy analysis yields a statistically significant result at an alpha level of 0.05 (2-sided), then the paired t-test will be performed at an alpha level of 0.05 for the key secondary endpoint.

Baseline for the key secondary analysis is the last evaluation prior to first dose of IMP in Treatment Phase A.

5.1.8.2 Analyses of Other Secondary Endpoints

Other secondary endpoints include:

- Percentage of subjects with an overly rapid increase in serum sodium level [REDACTED].
- Change in serum sodium level from 24 hours post-last dose to 7 days post-last dose.
- Percentage of subjects requiring rescue therapy (other than fluid restriction) during Treatment Phase A and Treatment Phase B.
- Percentage of subjects requiring fluid restriction during Treatment Phase A and Treatment Phase B.
- Pharmacodynamic endpoints are fluid intake, urine output, and fluid balance (intake minus output) every 6 hours on Days 1 and 2 in Treatment Phase A.

Descriptive statistics along with 2-sided 95% CIs will be applied for the percentage of subjects with an overly rapid increase in serum sodium and for the percentage of subjects requiring rescue therapy or fluid restriction.

The change in serum sodium level from 24 hours post-last dose to 7 days post-last dose will be summarized using a paired Student's t-test.

Urine volume will be summarized by 6-hour intervals using descriptive statistics. Fluid intake and the calculated value of fluid balance will be summarized for each 6-hour period and for the 24-hour daily interval on Days 1 and 2 in Treatment Phase A using descriptive statistics. A subgroup analysis by the disease etiology of hyponatremia or by fluid status (euvolemic, hypervolemic) may be conducted if there are sufficient subjects in each category.

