### **2.2.2 Secondary Objectives**

The key secondary objective is to assess the PK of tolvaptan and the effect on fluid balance in children and adolescent subjects with euvolemic or hypervolemic hyponatremia.

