### **3.7.4.3 Physical Examination**

Full and directed physical examinations will be performed and documented according to the schedule of assessments ([Section 3.7.1](#)). The initial physical examination should be a full physical. Subsequent physical examinations can be directed physical examinations that are focused on hyponatremia-related signs and symptoms as well as any major changes from baseline.

The principal investigator or his/her appointed designee is primarily responsible to perform the physical examination. If the appointed designee is to perform the physical examination, he/she must be permitted by local regulations. Whenever possible, the same individual should perform all physical examinations for a given subject. Any condition present at the post-treatment directed physical examination that was not present at Screening should be documented as an AE and followed to a satisfactory conclusion.

Full physical examination assessments should include assessments of all major body systems, including but not limited to, ears, nose, and throat, the thorax area, abdomen, urogenital, extremities, and skin and mucosae. Directed physical examinations should be focused on hyponatremia-related signs and symptoms as well as any major changes from baseline. Physical examination will include a fontanelle assessment as age appropriate. Neurological examinations will be performed in an age-appropriate manner per [Section 3.7.4.3.1](#).

Body weight will be measured predose each day throughout Treatment Phase A, Treatment Phase B and at each clinic visit in Follow-up Phase C, as possible. Every effort should be made to ensure that body weight measurements are performed in a reproducible and consistent manner. Body weight measurements should be performed at the clinical site always using the same scale. Subjects should wear the same type of clothes at each measurement, preferably a gown and no shoes. All body weight measurements should be taken post void.

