#### **3.7.4.7      Hyponatremia History**

Each subject's hyponatremia medical history will be recorded at screening. The hyponatremia history should include the etiology of subject's hyponatremia (including assessments per [Section 3.2.4.2](#)) and what treatment was administered prior to trial enrollment. Symptoms potentially attributable to hyponatremia should be specifically assessed for prior history. The hyponatremia assessment at Screening will consist of documentation of hyponatremia etiology (eg, HF, hepatocellular disease [including cirrhosis], SIADH/other), prior fluid intake and output, and prior hyponatremia treatment, ie, fluid restriction, if applicable. A detailed history specific to etiology of hyponatremia will also be recorded.

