### **6.2 Pharmacodynamic Analysis**

Urine volume will be summarized by 6-hour intervals using descriptive statistics. Fluid intake and the calculated value of fluid balance will be summarized for each 6-hour period and for the 24-hour daily interval on Days 1 and 2 in Treatment Phase A using descriptive statistics. A subgroup analysis by the disease etiology of hyponatremia or by

fluid status (euvolemic, hypervolemic) may be conducted if there are sufficient subjects in each category.

Urine osmolality and urine creatinine, potassium, and sodium concentrations will be summarized by collection interval and for zero to 24 hours on Days 1 and 2 in Treatment Phase A using descriptive statistics.

Missing urine concentrations or volumes will not be imputed. All calculations will use nominal times.

If urine volume during a collection interval is zero, then the amount excreted for that interval will be set to missing; values for 24 hours will be determined.

Correlations between urine output or fluid balance and change in serum sodium concentration may be explored graphically.

Correlations between tolvaptan AUC values and urine output on Day 1 may be explored graphically.

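### Fluid intake, urine output and fluid balance have no body-size scaling and no age or weight breakdown, although eligible weights run from 3 kg to above 50 kg

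*SAP*

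**What the plan says.** Protocol 2.2.2 sets as key secondary objective to "assess the PK of tolvaptan and the effect on fluid balance in children and adolescent subjects". The SAP lists the measures that answer the fluid part in 5.1.8.2: "Pharmacodynamic endpoints are fluid intake, urine output, and fluid balance (intake minus output) every 6 hours on Days 1 and 2".

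The analysis is descriptive. For urine, "Urine volume will be summarized by 6-hour intervals using descriptive statistics". For the other two, "Fluid intake and the calculated value of fluid balance will be summarized for each 6-hour period and for the 24-hour daily interval". Protocol 6.2 carries the same plan. The only subgroups named are etiology and fluid status, and both are optional.

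Elsewhere the plan does allow for size or age:

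- The acute kidney injury exclusion (protocol Table 3.4.3-1, criterion 9) judges urine output in mL/kg/h.
- Suspension doses are set in mg/kg (protocol Table 3.2.3-1).
- PK parameters are summarised by dose group and age group (protocol 6.1).
- SAP 5.1.4 and 5.2 break baseline and safety summaries down by age category.

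The data needed for scaling are collected: "Body weight will be measured predose each day throughout Treatment Phase A" (protocol 3.7.4.3).

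Timed fluid and urine collection begins at Hour 0, after dosing, and is scheduled on Days 1 and 2 only (protocol Table 3.7-1 and its footnote on intervals). Pre-dose fluid information appears only as a screening history item, "prior fluid intake and output, and prior hyponatremia treatment" (protocol 3.7.4.7). No analysis uses it.

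**The concern.** Fluid volumes in children rise with body size. If they are averaged in mL over infants and adolescents, the mean is pulled towards the heavier children and the SD contains the spread of body weight as well as the spread of response. A 6-hour balance of -100 mL is about 33 mL/kg at 3 kg (100/3) and 2 mL/kg at 50 kg (100/50), yet both enter the table as the same number.

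The plan deliberately enrols at least 25% of subjects under 6 years (protocol 3.3) and describes infants as especially vulnerable to electrolyte imbalance (protocol 1). Their per-kilogram response is what an unscaled pooled summary shows least well.

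The objective also speaks of an effect. The timed data contain no pre-dose interval and no untreated comparison, because all subjects take tolvaptan on Days 1 and 2 and randomization comes later. The tables can describe what happens on treatment but not how much of it is due to treatment.

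**Working it through.** The documents state no figure for these endpoints, so there is none to reproduce.

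**Weight range.** The lower limit is 3 kg (exclusion criterion 25). The top dosing band is above 50 kg with no cap (Table 3.2.3-1). Ratio: 50/3 = 16.7, so at least 16.7-fold.

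**One per-kg rate on the raw scale.** Take the protocol's own 0.5 mL/kg/h over 6 hours. Volume = 0.5 × 6 × weight: 9 mL at 3 kg, 60 mL at 20 kg, 150 mL at 50 kg. In mL/kg it is 3 at every weight.

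**Share of total volume.** Assumed weights (not in the documents): 25% uniform 3–20 kg, 25% uniform 20–35 kg, 50% uniform 35–70 kg.

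- Mean weight = 0.25 × 11.5 + 0.25 × 27.5 + 0.5 × 52.5 = 2.875 + 6.875 + 26.25 = 36.0 kg.
- At equal per-kg response, the youngest quarter supplies 2.875/36.0 = 8% of total volume and the heaviest half 26.25/36.0 = 73%.

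**Variance in urine volume due to weight.** Write volume = rate × weight, with the per-kg rate independent of weight.

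- Mean squared weight = 0.25 × 156.3 + 0.25 × 775 + 0.5 × 2858.3 = 1662. Variance = 1662 − 36² = 366. Squared CV of weight = 366/1296 = 0.282.
- Squared CV of volume = (1 + 0.282)(1 + k²) − 1, where k is the CV of the per-kg rate.
- R² of volume on weight = 0.282 / (squared CV of volume).

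| k | CV of raw volume | R² on weight |
|---|---|---|
| 0.4 | 0.70 | 0.58 |
| 0.6 | 0.86 | 0.38 |
| 0.8 | 1.05 | 0.26 |

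Weight explains more than half the variance only when k is below about 0.47. A simulation with different assumed weights (bands 3–20, 18–32 and 30–70 kg, in shares 25/25/50% or 50/25/25%) gives 48–57% at k = 0.5 and 26–34% at k = 0.8.

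**Variance in fluid balance due to weight.** The same formula applies with k = SD/|mean| of the per-kg balance. Five assumed pairs, in mL/kg/h:

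| Mean | SD | k | R² on weight |
|---|---|---|---|
| −2 | 1 | 0.5 | 0.47 |
| −1 | 1 | 1 | 0.18 |
| −2 | 2 | 1 | 0.18 |
| −1 | 2 | 2 | 0.05 |
| −0.5 | 1.5 | 3 | 0.02 |

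Under the alternative weight mixes the range is 2% to 57%, and it stays below 26% in four of the five settings. The sign of a child's balance does not depend on weight. The contribution to the pooled mean does: the heavier half supplies 73–77% of total balance in those mixes.

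**The case against.** The strongest objections, and what stands of each:

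- **Raw volume is inferred.** Neither document states a unit and no table shells are available. That is correct. But with no scaling rule, volume as measured is the natural reading, and a stated rule would remove the doubt.
- **A reader might infer that the tables mainly report body size.** The documents do not support this. They give no per-kg variability, and under the assumptions above weight explains most of the variance in urine output only at a per-kg CV below about one half. For fluid balance it is usually a minority.
- **A reader might infer that a large deficit in an infant would go unseen.** It need not. Volume status is assessed every 6 hours in Phase A (protocol 3.7.4.8), signs of dehydration are monitored (protocol 5.3.1.2), and hypovolemia or hypotension needing intervention is an event of special interest (SAP 5.2.2). Safety analyses are also run by age category (SAP 5.2).
- **Urine osmolality does not scale with size** and is summarised by interval (protocol 6.2, SAP 5.1.9.1). It informs on aquaresis but does not measure fluid balance.
- **The endpoints are descriptive and outside the testing hierarchy, and the trial ended early.** True, and this limits the weight of the point. It also means that converting the extra variance into a larger sample size answers no planned question. But SAP 5.1 keeps summary statistics, so these tables are still due. With very few subjects, one or two heavy children can dominate a mean in mL.
- **The screening record might seem to offer a ready baseline.** It does not. Protocol 3.7.4.7 gives no collection hours. Entry requires hyponatremia persisting despite background therapy that includes fluid restriction (inclusion criterion 2), whereas on treatment subjects must have access to water and restriction counts as rescue (protocol 3.2.4.3). A change from screening would mix the lifting of restriction with the drug effect.

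**Conclusion.** The point holds as a gap in specification. Across an eligible weight range of at least 16.7-fold, the plan gives the measures behind its fluid-balance objective no size scale and no age or weight breakdown, so pooled values in mL mix response with body size and lean towards heavier children. The 8% and 73% shares and the 26–58% for urine volume rest on an assumed weight mix and on a per-kg response unrelated to weight. That mix is the oldest that the age rule in protocol 3.3 permits, since its percentages are minimums. For fluid balance the share of variance due to weight is usually smaller.

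The timed data support a description of values on treatment, not a change or an effect. Importance is minor to moderate: the measures are secondary and descriptive, and no test or decision depends on them.

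**What to change.** In SAP 5.1.8.2, with protocol 6.2 read to match:

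1. Summarise fluid intake, urine volume and fluid balance as mL/kg for each 6-hour interval and for each 24-hour day, dividing by that day's predose weight. The plan now names a 24-hour summary for intake and balance but not for urine volume. State which weight is used if that day's is missing, for example the last earlier predose weight.
2. Present each summary overall and by the age categories the SAP already uses for baseline and safety. List raw mL by subject.
3. State that the results are on-treatment values on Days 1 and 2, that no timed pre-dose interval or untreated comparison exists, and that no change from baseline is reported. Do not use the screening intake and output history as a baseline.

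This is a free improvement: SAP wording and programming only. Weight and volumes are already collected, and no visit, sample or subject is added.

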5.1.8.3 Technical Computational Details for the Analysis of the Secondary Efficacy Endpoints

- 1) Percentage of subjects with an overly rapid increase in serum sodium level will only apply to the Treatment Phase A Efficacy Sample.
- 2) Change in serum sodium level from 24 hours post-last dose to 7 days post-last dose will only apply to the Treatment Phase B Efficacy Sample for responders.

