### **3.1.1.3 Follow-up Phase C**

All subjects will have an additional serum sodium measurement at 72 ( $\pm$  4) hours post-last dose and 7 (+ 1) days post-last dose. A final safety follow-up telephone contact/visit will be performed 14 (+ 2) days post-last dose.

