#### **3.5.3      Other Secondary Outcome Variables**

##### **3.5.3.1      Safety Variables**

The safety endpoints for all subjects include:

- Percentage of subjects with overly rapid increase in serum sodium level  
[REDACTED])
- Change in serum sodium level from 24 hours post-last dose to 7 days post-last dose
- Percentage of subjects requiring rescue therapy (other than fluid restriction) during Treatment Phase A and Treatment Phase B
- Percentage of subjects requiring fluid restriction during Treatment Phase A and Treatment Phase B
- Vital signs, blood pressure, clinical laboratory tests, body weight, and neurological examinations

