3.1 Treatment Phase A

All subjects will initially receive tolvaptan once daily on Days 1 and 2. If a subject's serum sodium level has not increased by at least 4 mEq/L (mmol/L) by end of Day 2, an additional day of treatment is required and is referred to as Day 2a. If subjects do not achieve an increase in serum sodium concentration of ≥ 4 mEq/L (mmol/L) on Day 2a, they will be defined as nonresponders. If subjects achieve an increase in serum sodium concentration of ≥ 4 mEq/L (mmol/L) on end of Day 2 (or 2a), they will be defined as responders.

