3.2 Treatment Phase B

On Day 3, responders will be randomized to either the Early Withdrawal group or the Late Withdrawal group. Subjects in the Late Withdrawal group continue tolvaptan treatment on Days 3 and 4, subjects in the Early Withdrawal group do not receive additional tolvaptan treatment on Days 3 and 4. Nonresponders will not be randomized.

For nonresponders from Treatment Phase A, the investigator will determine if the subject is to either:

- Continue treatment with IMP for Days 3 and 4, or
- Prescribe treatment per local standard of care for Days 3 and 4.

Randomization will be stratified by age [REDACTED], serum sodium response [REDACTED], and underlying hyponatremia etiology [REDACTED]
[REDACTED]

Subjects randomized to the Early Withdrawal group will be observed to determine whether additional intervention is required to maintain appropriate serum sodium levels. Subjects whose serum sodium declines by ≥ 4 mEq/L (mmol/L) or whose overall clinical condition requires further treatment to raise serum sodium levels should be treated per local standard of care. Any intervention intended to raise serum sodium concentration during the first 48 hours of Treatment Phase B (including fluid restriction) will be defined as rescue therapy. Subjects receiving rescue therapy will be considered to have reached their clinical endpoint, and their data will be censored from that time forward.

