5.1.1 Data Sets Analyzed

The following samples are defined for this trial:

- Treatment Phase A Safety Sample consists of all subjects who receive at least one dose of investigational medicinal product (IMP) in Treatment Phase A of the trial.
- Treatment Phase B Safety Sample for responders consists of all randomized Late Withdrawal subjects who receive at least one dose of IMP in Treatment Phase B of the trial and all randomized Early Withdrawal subjects.
- Treatment Phase B Safety Sample for nonresponders consists of all nonresponders who receive at least one dose of IMP or standard of care in Treatment Phase B of the trial.
- Treatment Phase A Efficacy Sample consists of all subjects who are in the Treatment Phase A Safety Sample and have baseline and at least one postbaseline serum sodium evaluation in Treatment Phase A.
- Treatment Phase B Efficacy Sample for the responders is based on the intent-to-treat (ITT) principle; the full analysis dataset will be composed of all subjects who are in the Treatment Phase B Safety Sample and have both baseline and at least one postrandomization serum sodium evaluation in Treatment Phase B.

- Treatment Phase B Efficacy Sample for the nonresponders consists of all subjects who are in the Treatment Phase B Safety Sample for nonresponders and have both baseline and at least one postbaseline serum sodium evaluation in Treatment Phase B.

The core dataset for efficacy analyses will be based on the ITT population. In order to handle missing data and restrictions imposed by different types of analyses (eg, change from baseline analysis), datasets derived from the ITT dataset will be used for the efficacy analyses.

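### The SAP limits the 24-hour to 7-day post-last-dose sodium change to randomized responders, while the protocol defines it as a safety endpoint for all subjects

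*SAP*

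**What the plan says.** Protocol 3.5.3.1 opens its list with "The safety endpoints for all subjects include", and the second item is "Change in serum sodium level from 24 hours post-last dose to 7 days post-last dose". Protocol 7.4.2.2 repeats the endpoint among the secondary safety outcomes, with a paired t-test and no stated restriction on population.

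SAP 5.1.8.2 carries the endpoint over with the same test. SAP 5.1.8.3, whose title refers to secondary efficacy endpoints, then states in item 2 that the endpoint "will only apply to the Treatment Phase B Efficacy Sample for responders". Under SAP 5.1.1 that sample is drawn from the matching safety sample, which is made up of randomized subjects only: Late Withdrawal children dosed at least once in Phase B, and everyone assigned to Early Withdrawal. SAP 3.2 adds: "Nonresponders will not be randomized".

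SAP 5.1.1 also defines a counterpart: "Treatment Phase B Efficacy Sample for the nonresponders consists of all subjects who are in the Treatment Phase B Safety Sample for nonresponders" with a baseline and at least one later sodium value in Phase B. It is not used for this endpoint.

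**The concern.** The endpoint describes the course of sodium once tolvaptan has stopped. The protocol asks this of everyone who took the drug. The SAP asks it only of subjects selected for a rise of at least 4 mEq/L in Phase A.

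That selection bears on the starting value. For Early Withdrawal subjects, the 24-hour post-last-dose reading is the trough at the end of Phase A, the point at which response is judged. Part of any later fall in that group may therefore be regression to the mean. The corresponding change in children who responded poorly, some after up to five doses, would not be reported. A reader who takes the protocol's definition at face value would assume that the table covers all subjects.

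**Working it through.** **1. Are nonresponders exposed?** Yes. SAP 3.1: "All subjects will initially receive tolvaptan once daily on Days 1 and 2". Those without the required rise must take a further dose on Day 2a, and SAP 3.2 lets the investigator continue tolvaptan on Days 3 and 4.

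**2. Are both values scheduled for them?**

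| Group | Last dose | 24-hour sample | 7-day sample |
|---|---|---|---|
| Early Withdrawal | Day 2 or 2a | Day 2 or 2a trough (Protocol 3.7.1.2.2, 3.7.1.2.3) | Yes |
| Late Withdrawal | Day 4 | Day 4 trough (Protocol 3.7.1.3.2) | Yes |
| Nonresponder, continuing | Day 4 | Day 4 trough (Protocol 3.7.1.3.2) | Yes |
| Nonresponder, standard of care | Day 2a | Day 2a trough (Protocol 3.7.1.2.3, item 9) | Yes |

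For the last column, Protocol 3.1.1.3 says "All subjects will have an additional serum sodium measurement at 72" hours after the last dose and, in the same sentence, at 7 days. Protocol 3.7.2.1 and its Table 3.7.2.1-1 agree. No new data are needed.

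**3. Is the change reported for nonresponders anywhere else?** No.
- SAP 5.1.9.1 compares the end of Phase B with the end of Phase A in nonresponders who continue.
- SAP 5.2.2 reports sodium of 145 mEq/L or more, overly rapid rise and worsening symptoms.
- SAP 5.2.3 summarizes laboratory changes from baseline.

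None of these is the change from 24 hours to 7 days after the last dose.

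**4. How many are left out?** The plan's 70 can be reproduced first. With difference 4, SD 5, two-sided alpha 0.05 and 90% power, the normal formula gives n per arm = 2 × (1.960 + 1.282)² × 25 / 16 = 32.8, so 33 per arm and 66 in total. The t-test version gives 33.8, so 34 per arm and 68 in total. At 35 per arm, power is 91.0% by the t-test. The planned 70 is consistent with this.

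Protocol 2.1 expects 100 subjects to yield 70 responders. Not randomized: 100 − 70 = 30, and 30 / 100 = 30%.

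**5. What could that do to a mean?** Let d be the difference in mean change between the omitted 30% and the responders. The all-subject mean then differs from the responder-only mean by 0.3 × d. The documents give no value for d, so these are assumptions:

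| Assumed d (mEq/L) | Shift in mean (mEq/L) |
|---|---|
| 1 | 0.3 |
| 2 | 0.6 |
| 4 | 1.2 |

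**The case against.** **Early termination.** SAP 5.1 says that, given extremely low enrollment and early termination, the efficacy analyses reduce to summary statistics. The paired t-test need not be run. This stands and lowers the stakes, but it does not lift the population rule, which would still govern the summary.

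**A responder-only question is cleaner.** Nonresponders who stop are treated per standard of care on Days 3 and 4, inside the 24-hour to 7-day window, so their change mixes withdrawal with new treatment. This stands as a reason not to lead with a pooled row. It does not justify an unexplained omission, and the Early Withdrawal window is not free of treatment either, because rescue is allowed there.

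**The protocol is not fully consistent.** Protocol 7.4.2.2 names no population. Protocol 7.6 relies on the Safety Samples, and the Phase B one in Protocol 7.2 contains only randomized subjects. This is fair, and those definitions also need aligning. It does not override the explicit wording of 3.5.3.1, and the Phase A Safety Sample covers every dosed subject.

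**A stronger reading.** A reader might infer that nonresponders drop out of safety reporting altogether. The documents do not support that. SAP 5.1.1 adds safety and efficacy samples for nonresponders, SAP 5.2 uses the Safety Samples, and the key secondary endpoint covers all Phase A subjects with the required values. The gap is confined to one endpoint.

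**Conclusion.** The two documents give different populations for the same endpoint, and the SAP offers no justification. Following the SAP would not produce the endpoint that the protocol defines.

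The size is about 30 of 100 subjects on planning figures. This assumes that all 100 are dosed and 70 are randomized. A reader might take the 30 to be nonresponders, or to be the number actually omitted. Neither follows. The 30 includes anyone not randomized, such as children who leave or receive rescue in Phase A. Protocol 7.2 counts as enrolled everyone with a signed consent or assent form, so fewer than 100 may be dosed, and the omitted count then falls one for one. Actual enrollment is not given. In the other direction, the rule also drops randomized subjects with no post-randomization sodium value.

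The shifts of 0.3 to 1.2 mEq/L rest on assumed differences. They illustrate scale and do not predict a bias. With only summary statistics now required, this is a correction to a descriptive secondary safety endpoint and does not touch the primary result.

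**What to change.** In SAP 5.1.8.3, item 2, apply the endpoint to all subjects in the Treatment Phase A Safety Sample who have both the 24-hour and the 7-day post-last-dose sodium values. Report it descriptively, in line with SAP 5.1, in four rows: Early Withdrawal, Late Withdrawal, nonresponders continuing tolvaptan, and nonresponders on standard of care. These rows should be the main presentation. If a pooled row is added, footnote that standard-of-care treatment falls inside the window for nonresponders who stopped. Dosed subjects who left before a Phase B group was assigned but have both values can be listed.

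If the sponsor prefers to keep the responder-only population, the SAP should state it as a departure from Protocol 3.5.3.1 and give the reason.

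The cost is one sentence and a slightly wider table. The downside is that some rows will be small. No new samples, visits or change in sample size are needed.
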